7.2 General study design and justification of design

An assessor-blinded, randomized crossover study design will be applied. Each patient will undergo each of the two treatments (A-B) listed below. Furthermore, patients will be randomized to either receive placebo education or to not receive placebo education (e.g. B_1 = placebo education; B_2 = no placebo education). In other words, each patient will receive one of the two following treatment sets: either (A, B_1) or (A, B_2); the individual components of these sets will be randomized.

TREATMENT	General (visible)	Open drug application	
A→ No treatment	Infusion RL	No	
intervention	Infusion rate: 100ml/h		

B _{1,2} →Open-label	Infusion RL	OLP
Placebo alone	Infusion rate: 100ml/h	

Table 1: Overview study interventions

In each treatment the patient will receive a standard infusion containing only Ringer lactate (RL) infused at a rate of 100ml/h. The purpose of this infusion is simply to keep venous access.

To avoid any systematic bias the assignment of the study groups will be performed in a balanced randomized manner. To control for excitement and habituation effects we operate the interventions in a randomized order in every participant.

The participants are recruited by an advertisement on the University of Basel homepage and eligible volunteers will be included on a "first come, first served" basis.

Study participants are orally and written informed about study aims and interventions before the first assessment.

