11.1 Hypothesis

Main hypotheses

We first hypothesize that open label placebo administration leads to a significant reduction in the area under the pain curve (AUPC) from minute 40 to minute 100 compared to no open-label placebo in induced acute pain in healthy male adults (i.e. $B_{1/2}$ vs. A)

Secondary Hypotheses

Secondly, we hypothesize that education and conditioning further reduce the AUPC in the same period of time compared to those patients receiving open-label placebo without education in induced acute pain in healthy male adults (i.e. B_2 vs. B_1).

Finally, we hypothesize that the observed differences in the AUPC will be reflected in both hyperalgesia and allodynia as well as by biomarkers.

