11.2 Determination of sample size

Sample size has been determined by a Wilcoxon signed-rank test for the AUPC for Treatments A and B. The AUPC is the product of the NRS x Time. 7 measurements of NRS will be made in total, one every ten minutes. We expect the area under the curve to be 50 NRSxminutes based on a general difference of 1 NRS point and some time for the effect to fully develop. We expect the standard deviations in both groups to be 1 NRS or 60 NRS*min. Using a t-test with a 20% mark-up for non-parametric data we have arrived at a required number of patients of 22. However since 20-30% of participants can be expected to be non-responders to placebo [38] and expecting 10% drop out we have arrived at a total number of patients to be recruited of 32.

11.3 Statistical criteria of termination of the trail:

Upon completion. With such a small sample size, no interim analysis will be conducted.

11.4 Planned Analyses, Datasets, and Analysis Populations:

For the first hypothesis (AUPC for $B_{1/2}$ vs. A) we will conduct a Wilcoxon signed-rank test. Additionally, we conduct a mixed effects model using the AUPC as the dependent outcome and the treatment, the session order (e.g. Treatment B before Treatment A) time during electrical stimulation (in minutes), and finally the individual. This will allow for a more differentiated analysis accounting for temporal and sessional habituation in explaining the treatment effect.

For the effect of education, we will compare the AUPC of: Treatment B_1 vs Treatment B_2 , again by a Wilcoxon signed-rank test.

The outcomes hyperalgesia and allodynia, as well as biomarkers will be examined analogously to the respective comparisons with the AUPC.

11.8 Interim analysis:

Given the small sample size and limited time, no interim analysis will be conducted.

11.9 Safety analysis:

None. However, patients will be under the continuous surveillance of anesthesiology staff.

11.10 Deviation(s) from the original statistical plan:

The statistical plan will be published prior to commencement on clinicaltrials.gov. Any deviations from the statistical plan will be reported and justified in the final report.

11.11 Handling of missing data and drop outs:

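### The education comparison names a paired test for two different groups of people and leaves each participant's own no-treatment session unused

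*Combined protocol and SAP*

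**What the plan says.** Section 7.2 describes a crossover of no treatment (A) against open-label placebo (B), with education randomised on top: "each patient will receive one of the two following treatment sets", namely A with B1 (educated) or A with B2 (not educated). No participant contributes to both B1 and B2, and every participant has a session A. The same section says that "the assignment of the study groups will be performed in a balanced randomized manner".

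Section 11.1 states the education hypothesis as a further reduction in AUPC "compared to those patients receiving open-label placebo without education", that is, B2 vs B1.

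Section 11.4 gives one test for it, which opens "For the effect of education, we will compare the AUPC of" and continues "Treatment B_1 vs Treatment B_2 , again by a Wilcoxon signed-rank test". Under the first hypothesis (placebo vs no treatment) the same section adds a model: "Additionally, we conduct a mixed effects model using the AUPC as the dependent outcome and the treatment, the session order", followed by time during stimulation and the individual. Neither education nor an education-by-treatment term is listed. Hyperalgesia, allodynia and biomarkers are to be handled in the same way as AUPC.

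Section 11.2 sizes the trial for A vs B only. It gives no effect size or power for education.

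**The concern.** Two things in the education sentence need attention.

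First, a signed-rank test needs pairs, and there are none between B1 and B2. The sentence has to be rewritten whatever else is decided.

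Second, a two-sample comparison of session-B values carries all the between-person variation in pain rating. Session A was measured in the same people with the same model and could absorb some of that variation without new data. Session A is also the only information in the trial that can show whether education strengthens the response to placebo (B relative to A) or lowers ratings in both sessions. The plan never compares A between the education groups.

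What is at stake is the precision and interpretation of a stated secondary objective, and of the other outcomes that inherit the same analysis. The primary comparison is not affected.

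**Working it through.** **Inputs from the plan (11.2).** AUPC SD 60 NRS×min under each treatment; A–B difference 50; 20% mark-up for nonparametric data; 22 required, 32 recruited.

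**Assumptions (not in the plan).** Two-sided 5%; 1:1 split of 32, so 16 per education group; A–B correlation ρ of 0.3 to 0.7; education difference of 50, borrowed from the A-vs-B figure.

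**Reproducing the plan's 22.** The SD of a paired difference is 60·√(2(1−ρ)).
- ρ = 0.5: SD 60.0. A paired t-test at 90% power needs 18; 18 × 1.2 = 21.6, so 22.
- ρ = 0.3: SD 71.0. A paired t-test at 80% power needs 18; again 21.6, so 22.

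The plan states neither power nor correlation, so its 22 does not fix ρ.

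**Standard errors for the education contrast, 16 vs 16.**
- Unadjusted B1 vs B2: 60·√(2/16) = 21.2.
- Session-B AUPC adjusted for own session A: 21.2·√(1−ρ²), times √(1 + 1/28) for estimating the slope, with 29 rather than 30 df. At ρ = 0.5: 21.2 × 0.866 × 1.018 = 18.7.
- Education-by-treatment term: with two sessions per person this is the group difference in B−A, so 21.2·√(2(1−ρ)). At ρ = 0.5: 21.2.

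**Power for a difference of 50 (noncentral t).**

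| ρ | Unadjusted | Session-A covariate | Education × treatment |
|---|---|---|---|
| 0.3 | 63% | 65% | 49% |
| 0.5 | 63% | 73% | 63% |
| 0.7 | 63% | 88% | 84% |

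Putting session order in the covariate model as well costs up to about 2 points (about 63%, 72% and 87%). For a difference of 25, power is 21% unadjusted and 25% with the covariate at ρ = 0.5.

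**95% half-width at ρ = 0.5.** Unadjusted: 2.04 × 21.2 ≈ 43. Adjusted: 2.05 × 18.7 ≈ 38 NRS×min.

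**Where the covariate starts to pay.** It needs (1−ρ²)(1 + 1/28) < 1, so ρ² > 1/29 and ρ > about 0.19.

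**What the covariate model does not separate.** Suppose education lowers ratings by 20 in both sessions and has no effect on the placebo response. With equal SDs the slope on session A is ρ, so the adjusted difference is still 20(1−ρ): 14, 10 and 6 at ρ = 0.3, 0.5 and 0.7. Adjustment removes only part of a uniform shift. The education-by-treatment term removes all of it.

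**The case against.** The strongest defence is that the raw contrast answers the question asked. Section 11.1 poses B2 vs B1, education is randomised, and an unadjusted two-sample comparison is unbiased for that effect. This stands, and it is why the unadjusted comparison should be kept. A reader might infer that comparing session-B values alone is biased; the documents do not support that.

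Session A is also not a baseline. Education is given before the first session (7.4), and treatment order is randomised, so in some participants A also follows B. Conditioning on it assumes that education leaves session-A pain unchanged. This stands too, and limits the covariate model to a supporting role unless the plan argues otherwise.

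The gain may be small. The current is calibrated to NRS 6 in every session (7.7), which may shrink the stable between-person variation that session A could explain. At ρ = 0.3, which also reproduces the plan's 22, the gain is about 2 points.

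Finally, the synopsis promises a mixed model in general terms, which could be read as covering education. It names only order and time, and 11.4 places the model under the first hypothesis. At best this is an ambiguity to be resolved.

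None of this rescues the signed-rank test.

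**Conclusion.** The point holds as a should-fix on a secondary objective. The paired test cannot be run on B1 and B2, and the plan leaves session A out of the education analysis although everyone has it.

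The size of the gain depends on a correlation the plan does not state: about 2 points of power at ρ = 0.3, 11 at 0.5 and 25 at 0.7, and none below about 0.2. These figures rest on SD 60, 16 per group, two-sided 5% and a borrowed difference of 50. A smaller education effect would leave power low either way.

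Three stronger readings are tempting and are not supported:
- That an education-by-treatment term gives the same precision as the covariate model. It has no more power than the raw comparison at ρ = 0.5 and less below it.
- That the covariate model isolates education's effect on the placebo response. It does so only if education does not change session A.
- That the plan itself implies ρ = 0.5. A value of 0.3 with 80% power fits its 22 equally well.

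**What to change.** Replace the education sentence in 11.4 with three analyses, each tied to its purpose:

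1. An unadjusted two-sample comparison of session-B AUPC, B1 vs B2 (for example a rank-sum test), which matches 11.1.
2. For precision, a between-person model of session-B AUPC on education, session order and own session-A AUPC, reported beside the unadjusted result with a note that session A is measured after education.
3. For interpretation, education and education × treatment added to the mixed model, to show whether education changes the B-minus-A response or lowers ratings in both sessions.

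State in advance which is the main education analysis, and carry the same choice to hyperalgesia, allodynia and biomarkers. Record the assumed A–B correlation and education effect, with a range.

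The cost is SAP wording, with no extra participants or measurements. The one real downside, adjustment for a post-education measure, is contained by showing both results.

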5.2 Secondary outcomes

- The pain response measured by the AUPC (NRS every 10 minutes during electrical stimulation) will be used for further comparison of the two different treatment interventions every participant recieves during the study. We compare the participants received a education about placebo to the non prior educated participants.
- 2. Hyperalgesia and allodynia will be measured analogously to the NRS as above.
- 3. Saliva concentration of cortisol, measured at baseline, 30, 60 and 100 minutes after pain induction.

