7.5 Experimental design

Acute pain will be induced through electrical stimulation in an established model first described by [name] et al.[16]. (For detailed experimental setup cp. Chapter 7.6-7.7)

Before the first intervention participants will be randomized to:

- 1) A placebo education group
- 2) A non-placebo education group

Participants in both groups will undergo the pain model two times. Every participant will receive treatment as follows in a sequential cross-over design (cp fig. 1).

[figure not shown]

Figure 1: Experimental design

During every experiment levels of saliva cortisol levels are collected at baseline, 30min, 60min and 100min after pain induction (cp. Fig. 4).

A washout period of two weeks well be instituted to prevent contamination (cp. Fig 1).

Randomization as well as preparation and application of the hidden and not hidden study medication will be executed by study stuff not involved in assessments during the intervention. During the individual experiment pain scores, hyperalgesia and allodynia will be assessed and documented by an investigator blinded to the treatment group.

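### The education comparison (B_1 vs B_2) is assigned a paired signed-rank test, but the two sets of values come from different people

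*Combined protocol and SAP*

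**What the plan says.** Section 11.4 of the combined protocol and SAP names a Wilcoxon signed-rank test for placebo against no treatment (B vs A). It then turns to education: "we will compare the AUPC of: Treatment B_1 vs Treatment B_2 , again by a Wilcoxon signed-rank test". A further sentence extends the same approach to the other outcomes: "The outcomes hyperalgesia and allodynia, as well as biomarkers will be examined analogously to the respective comparisons with the AUPC".

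The design sections describe education as a factor that differs between people:

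- Section 7.2: "patients will be randomized to either receive placebo education or to not receive placebo education", and so "each patient will receive one of the two following treatment sets: either (A, B_1) or (A, B_2").
- Section 7.5 places this allocation ahead of the first session ("Before the first intervention participants will be randomized to" an education or a non-education group) and adds: "Participants in both groups will undergo the pain model two times". Those two sessions are A and B.
- Section 5.2, on the secondary outcome: "We compare the participants received a education about placebo to the non prior educated participants".
- Section 11.1 words the education hypothesis as a contrast with other patients: "compared to those patients receiving open-label placebo without education".

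**The concern.** The signed-rank test ranks within-pair differences. For B vs A the pairs exist, because each participant has both sessions. For B_1 vs B_2 there are none. To run the named test, someone would have to pair strangers, for example by study number, and the p-value would then depend on that choice.

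This is the only test named for the first secondary hypothesis. The mixed model in 11.4 lists treatment, session order, time and individual. It names neither education group nor a treatment-by-education term, so it does not clearly supply a valid alternative. The extension to the other outcomes carries the same fault into the education contrasts for hyperalgesia, allodynia and cortisol.

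Section 7.11 opens the randomisation code to the analysis staff after the last session. An unspecified pairing would therefore be chosen with outcomes and group membership both in view.

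The plan also compares B sessions alone. It makes no use of each participant's own no-treatment session, which would show whether education changes the placebo effect itself.

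**Working it through.** **Step 1: are there pairs?** Under 7.2 a participant contributes either (A, B_1) or (A, B_2). The only within-person pair is A with B. The number of participants with both B_1 and B_2 is zero, and no section matches people across the education groups.

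**Step 2: the plan's own inputs.** Section 11.2 gives a difference of 50 NRS x min, an SD of 60 NRS x min per condition, and 22 participants for B vs A. It gives no figure for B_1 vs B_2. The 22 can be reproduced if one assumes two-sided alpha 0.05, 90% power and a within-person correlation of 0.5, none of which is stated:

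- SD of the difference = 60 x sqrt(2 x (1 - 0.5)) = 60.
- Paired t-test for 50/60: n = 17.2, rounded up to 18; 18 x 1.2 = 21.6, so 22.
- 22 x 1.3 = 28.6, so 29; 29 x 1.1 = 31.9, so 32.

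Other combinations come close (80% power with correlation 0.25 gives 23). The sample size covers the paired comparison only.

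**Step 3: how far does the pairing matter?** Inputs: normal AUPC values, SD 60 (section 11.2), 16 vs 16 (assumed; 7.2 says only that assignment is balanced), two-sided 5% level (assumed). The documents give no education effect, so 50 (the plan's placebo effect), 25 and 0 are shown. In each simulated data set the two groups were paired at random 100 times and the signed-rank test was run on each pairing.

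| Assumed education effect (NRS x min) | Verdict depends on pairing: 5% to 95% of pairings significant | At least one pairing significant and at least one not |
|---|---|---|
| 50 | about 40% of data sets (34% to 42% across runs) | 59% |
| 25 | 20% to 30% | 38% |
| 0 | 10% to 12% | 21% |

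At an effect of 50, the median 5th and 95th percentiles of p over pairings were 0.008 and 0.093 (0.007 and 0.074 in another run). The median smallest and largest p were 0.002 and 0.13.

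**Step 4: error rate and power.** With equal groups and one arbitrary pairing, the signed-rank test rejects in 4.9% of data sets under no effect, against 4.8% for the rank-sum test. At an effect of 50, power is 54% to 56%, against 59% to 60% for rank-sum.

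**Step 5: unequal groups.** With 16 and 15 the paired test cannot be computed. With 16 and 13, as an illustration, 16 - 13 = 3 participants would have to be discarded.

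**Step 6: what the correct test can deliver.** For 16 vs 16 and an effect of 50, the standard error is 60 x sqrt(2/16) = 21.2 and 50/21.2 = 2.36. Normal-theory power is Phi(2.36 - 1.96) = 65%; the two-sample t-test gives 63% and the simulated rank-sum test 59%. For an effect of 25 the figures are 22%, 21% and 20%. For 80% power at 50, the t-test needs 24 per group. With the plan's 20% mark-up this is 24 x 1.2 = 28.8, so 29 per group or 58 in total, against 32 planned.

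**The case against.** The strongest reply is that this is a slip in naming a test and does little harm. The synopsis calls the simple tests generally paired, 11.11 speaks of most tests being paired, and 5.2 describes a comparison of two groups of people, so the authors evidently expected an unpaired test somewhere. A random pairing fixed in advance keeps type I error near 5% and costs only a few points of power. The primary comparison is untouched. All of this is true, and it limits the consequences. It does not supply a test: 11.4 names no unpaired method and fixes no pairing.

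Further points have some force:

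- The effect of 50 is the plan's figure for placebo against no treatment. The education effect is an additional reduction and may be smaller, so the 40% lies at the upper end of the range shown.
- Drop-outs are to be replaced (9.4, 11.11), so 16 vs 13 is hypothetical. But replacement within the same education group is not stated, and 11.11 also says that data available at drop-out will be analysed, so unequal groups remain possible.
- The synopsis promises a mixed model in addition to the simple tests. A three-level treatment term (A, B_1, B_2) is a conceivable reading, but 11.4 does not say so.
- For the other outcomes, the B vs A tests remain correctly paired; only the education contrasts are affected.
- Comparing B minus A between groups answers a different question from the hypothesis in 11.1. Because education precedes both sessions, it estimates the treatment-by-education interaction. It gains power only if the within-person correlation exceeds 0.5, which the documents do not state. It is a supplement, and the main point does not depend on it.

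**Conclusion.** The concern holds. The test named for the education hypothesis cannot be carried out as written, because the design produces no B_1/B_2 pairs. Any pairing would be arbitrary, and under the plan's SD with 16 per group it would decide significance in roughly 10% to 40% of data sets as the education effect goes from 0 to 50 NRS x min. That range rests on normal data, an equal split, a two-sided 5% level and assumed education effects.

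The damage is confined to the first secondary hypothesis and its counterparts for hyperalgesia, allodynia and cortisol. Neither type I inflation nor power loss is the issue; the issue is a p-value that depends on an unspecified analyst choice. It must be corrected before analysis, because 11.10 commits to publishing the plan in advance and justifying deviations, and a test chosen after unblinding would be a deviation of that kind.

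**What to change.** In section 11.4, for B_1 vs B_2, replace the signed-rank test with the Wilcoxon rank-sum (Mann-Whitney) test between the educated and non-educated groups. State that it applies to AUPC and to the education contrasts of hyperalgesia, allodynia and cortisol, and that the B vs A tests stay paired. The rank-sum test accepts unequal groups.

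As a supplement, compare each participant's AUPC in B minus AUPC in A between the groups by rank-sum, or add education and a treatment-by-education term to the mixed model. If this is included, state that the rank-sum test on the B sessions decides the hypothesis in 11.1 and that the supplement addresses whether education changes the placebo effect.

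The cost is SAP wording only, with no extra data, visits or participants. The change does not remedy the limited power for education: about 59% by rank-sum if education adds a full 50 NRS x min, and about 20% if it adds 25.

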- To investigate the effect of education prior to an open label placebo application.
- To investigate the effect of open label placebo application on biomarkers of stress (saliva cortisol)

Outcome(s):

[figure not shown]
Primary outcome:

Pain response measured by the Area under the Pain Curve (AUPC) using the numeric rating scale (NRS) from minute 30 to 100 after inducing definded pain in an experimental setting. Main comparison: The effect of open label placebo v.s. no treatment intervention.

Secondary outcomes:

 The pain response measured by the AUPC (NRS every 10 minutes during electrical stimulation) will be used for further comparison of the two different treatment interventions every participant recieves during the study.

	 Regularly taking medication potentially interfere with pain sensitation (analgesics, antihistamines and calcium and potassium channel blockers) Neuropathy Chronic pain Neuromuscular or psychiatric disease Known or suspected kidney or liver disease 		
Measurements and procedures:	Healthy male adults are recruted via an advertisment on the homepage of the University of Basel. After informed consent, but before any intervention, the participiants are randomized to a placebo educated and a non-educated group. The education group will receive an education about placebos and their effects prior to study intervention during the placebo will be applied. Every participiant will pass trough two interventions with electrical induced pain, defined at a NRS of six for 100 minutes each. Between the sessions a minimal two weeks washout period will be hold. During the two interventions participiants beceive the following treatments delineated above in a randomized manner.		
Study medication/ Study product:	Intravenous application of: open label placebo (2ml saline 0.9%).		
Control intervention	During one intervention (A) we do not apply any treatment at all during the intervention time. This to control for habitation effects during current application and create a comparison.		
Number of Participants with Rationale:	Based on our sample size calculation, we will require 22 participants. Recent estimates state that some 20-30% of patients are placebo-non-responders. Consequently, we will include 29 patients. However, with an estimated drop-out of 10% we plan to recruit 32 paitents. Patients dropping out will be replaced.		

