5.1 Primary outcome

Pain response measured by the Area under the Pain Curve (AUPC) using the numeric rating scale (NRS) from minute 40 to100 after inducing definded pain in an experimental setting. Main comparison: The effect of open label placebo v.s. no treatment intervention.

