7.12 Collection and processing of biomarkers

Saliva collection and processing

Oral fluids are collected to measure cortisol levels in response to induced pain. To control for diurnal variations of neuroendocrine parameters all experiments will be carried out between 4pm and 7pm.

Consistent with the procedures incorporated be Dickerson et al. [35] we decided to obtain the biological parameters in this study from oral fluids. Saliva levels of cortisol [36] are reliable and highly correlated with plasma levels. Therefore it is a less reactive, less invasive but reliable method to measure neuroendocrine immune activity.

To ensure a non-contaminated measurement participants are asked:

- Not to use non-prescription medications or alcohol within 24 hours before measurement
- To refrain from exercise and caffeine at least 2 hours to testing session
- Not to eat foods that may cause bleeding of the gums (e.g. potato chips) or brush their teeth for at least 2 hours prior to testing session.

Collection of saliva for cortisol determinations

A collection device (Salivette®) is placed into the mouth on the top of the tongue for 2.5min per sampling time point. Cortisol in saliva is in its unbound biologically active form and its concentration is independent of saliva flow rate [37].

Time points of measurements

Basic value:

After arrival of the participant for the intervention a 15 min rest must be hold before the first collection. The first collection during the first experimental intervention is to make the participant familiar with the procedure and will not be used for later analyses. A second collection will be performed directly after the test collection.

Further collections:

Saliva will be further collected as follows during the experimental intervention (cp. figure 4):

- 1. 30 min after constant electrical stimulation before application of study medication
- 2. 30 min after completed application of the study medication
- 3. 60 min after completed application of the study medication

After collection the oral fluids samples are immediately refrigerated before being transferred and will be stored at -80°C until further analysis, if analysis cannot be performed within 6 hours after collection.

[figure not shown]

Figure 4: Schedule for measurement of pain, hyperalgesia, allodynia, biomarker collection and application of study medication during an individual study intervention session.

8. Medical products and Medications used during the study

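### The cortisol comparison gives no role to the sample taken just before placebo, and the AUPC rule it borrows can be read so that pre-placebo samples enter the contrast

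*Combined protocol and SAP*

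**What the plan says.** Section 5.2 lists cortisol as a secondary outcome: "Saliva concentration of cortisol, measured at baseline, 30, 60 and 100 minutes after pain induction". Section 7.12 describes the middle sample as taken "30 min after constant electrical stimulation before application of study medication", and places the last two at 30 and 60 minutes after the application is complete.

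The whole cortisol analysis is one sentence in section 11.4: "The outcomes hyperalgesia and allodynia, as well as biomarkers will be examined analogously to the respective comparisons with the AUPC". The AUPC comparison it points to has two parts. One is a Wilcoxon signed-rank test of B against A. The other is a mixed model with treatment, session order, time during stimulation and individual. No baseline term and no treatment-by-time term is listed.

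The AUPC window is "from minute 40 to minute 100" in section 11.1, and section 5.1 agrees ("using the numeric rating scale (NRS) from minute 40 to100 after inducing definded pain"). The synopsis differs: "using the numeric rating scale (NRS) from minute 30 to 100 after inducing definded pain in an experimental setting". No section defines a cortisol summary, window or baseline.

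**The concern.** The AUPC rule was built for a rating made every ten minutes after the point at which placebo may be given. Cortisol has four widely spaced samples, two of them taken before that point. Carrying the rule over raises two questions.

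- Which samples enter the contrast? A sample taken before the injection cannot respond to it. Pooling such a sample adds noise to the B minus A difference and no signal.
- What is the minute-30 sample for? It is the natural pre-treatment value for its session, and the stated analysis never uses it that way.

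At stake is the sensitivity of a named secondary objective, the effect of open-label placebo on a stress biomarker, in a trial of 32 volunteers. The choice of samples could also be made after the data are seen.

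**Working it through.** **The plan's own count.** Section 11.2 states: "7 measurements of NRS will be made in total, one every ten minutes". Ratings at 40, 50, …, 100 number 7, which matches the 40 to 100 window. Ratings at 30, 40, …, 100 would number 8.

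**Inputs.** Cortisol times are 0, 30, 60 and 100 (section 5.2, taking baseline as minute 0). Section 7.9 gives placebo 30 minutes after calibration. On that clock the section 7.12 times are about 0, 30, 60 and 90. The minute-0 and minute-30 samples precede placebo.

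**Formula.** The trapezoid weight of a sample is half the length of each interval it borders within the window.

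| Reading | Weights (0 / 30 / 60 / last) | Share on pre-placebo samples |
|---|---|---|
| 40–100, samples inside the window only | – / – / 20 / 20 | 0% |
| 40–100, value at minute 40 interpolated | – / 6.67 / 33.33 / 20 | 6.67/60 = 11% |
| 30–100 (synopsis) | – / 15 / 35 / 20 | 15/70 = 21% |
| Full session, section 5.2 times | 15 / 30 / 35 / 20 | 45/100 = 45% |
| Full session, section 7.12 times | 15 / 30 / 30 / 15 | 45/90 = 50% |

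With section 7.12 times the second interval-based window (30 to last sample) gives 15/60 = 25%.

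**First row.** The area is 20·C60 + 20·C100, which is 40 times the mean of the two post-placebo samples. A signed-rank test on this area and on that mean give the same result.

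**Mixed model on all four samples.** With complete data and no treatment-by-time term, the treatment coefficient is the equally weighted average of four B minus A differences. Two of the four (50%) are pre-placebo.

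**Effect on sensitivity (assumptions, not in the documents).** Let the B minus A differences have equal variances and correlation ρ from 0 to 0.9 between samples, with a constant effect after placebo. The standardised effect relative to that of the two post-placebo samples is:

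- 30–100: 0.79 to 0.90
- full-session area: 0.51 to 0.74
- four-sample mixed model: √[(1+ρ) / (2(1+3ρ))], which is 0.71 at ρ = 0 and 0.51 at ρ = 0.9

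As an illustration, take a paired standardised effect of 0.6 and n = 22. Power is 77% with the two post-placebo samples, 56 to 68% for 30–100, and 27 to 51% for the full-session area.

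**What the unused baseline could be worth.** Under the same assumptions with equal correlations, adjusting the post-placebo mean for the minute-30 difference multiplies its variance by 1 − 2ρ²/(1+ρ):

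- ρ = 0: 1.00
- ρ = 0.3: 1 − 0.18/1.3 = 0.86
- ρ = 0.5: 1 − 0.5/1.5 = 0.67
- ρ = 0.7: 1 − 0.98/1.7 = 0.42

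The gain therefore runs from nothing to large, and the documents give no ρ with which to place it.

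**The case against.** The most natural meaning of an analogous analysis keeps the 40 to 100 window. That window holds exactly the two post-placebo samples, so nothing is diluted. This stands.

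A reader might infer that the plan, as written, shrinks the cortisol effect to about half. The documents do not support that. No section plans a full-session cortisol area, so 45 to 50% is the outer case among several readings. An area in concentration × time does not shrink anyway: a constant effect d contributes 35d + 20d = 55d over the full session and 40d over 60 to 100. The loss lies in the standardised effect, and its size needs the assumptions above.

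A reader might also infer bias. Session order is randomised, so leaving out the baseline costs precision and does not bias B against A. The mixed model already carries session order. Section 7.12 confines experiments to 4pm to 7pm, which limits diurnal variation. It does not remove it: preparation plus intervention takes 30 + 100 = 130 minutes, so start times within a 180-minute slot can differ by up to 50 minutes between visits.

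One qualification concerns the baseline itself. Section 7.3 tells every participant that placebo comes in one session and not in the other. He can therefore work out the second session's treatment, and the minute-30 sample there may reflect anticipation. Adjustment then isolates the effect of the administration. This is a reason to report the unadjusted comparison beside it.

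Two things survive: under no reading does the minute-30 sample serve as a baseline, and section 11.4 does not say which reading applies.

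**Conclusion.** The point holds as a low-cost improvement to a secondary outcome. It is not an error in the main analysis, and the primary AUPC comparison is untouched.

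Under the 40 to 100 window there is no dilution. The possible loss is precision from an unused pre-treatment value, of a size the documents do not allow one to fix. Under wider readings, samples that cannot respond to the injection carry about 21% of the weight (synopsis window), 45 to 50% (full-session area) or half (mixed model on all four samples).

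The shares rest on trapezoid weights, on baseline taken as minute 0 for the full-session rows, and on placebo at about minute 30. They are weights on samples; the time before placebo is 30 of 100 minutes. The standardised effects and power figures rest on assumed variances, correlations and effect size.

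**What to change.** In section 11.4, before unblinding:

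1. Define the cortisol outcome as the mean of the two post-placebo samples in each session.
2. Compare B with A by regressing the within-person B minus A difference in that mean on the B minus A difference in the minute-30 sample, with session order in the model (coded so that the intercept is the treatment effect averaged over the two orders).
3. Keep the signed-rank test on the post-placebo mean as a sensitivity analysis.
4. Reconcile the last sampling time (minute 100 in section 5.2, 60 minutes after application in section 7.12) and the AUPC window (30 to 100 in the synopsis, 40 to 100 in sections 5.1 and 11.1).

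The cost is SAP wording and about one degree of freedom for the baseline term, since session order is already in the planned model. No sample, visit or participant is added.
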